10.2.20. Motor Function Tests – Ambulatory Subjects Only

Motor function tests will be performed at Baseline for all subjects, at the end of Stage 2 for Cohort 1, every 3 months in Stage 3 and every 6 months in Stage 4 for all subjects in the order indicated in [Table 9](#), [Table 10](#), [Table 11](#), [Table 12](#), and [Table 13](#). Motor function tests can be performed between Day -7 and Day 0 for baseline measures. Detailed instructions for these tests/assessments will be provided in a separate study procedure manual(s).

10.2.20.1. 6-Minute Walk Test (6MWT)

The objective of the 6MWT is to walk (not run or jog) as far as possible for 6 minutes. The timed walk test should be performed with walking shoes on a flat surface.

In the event of an invalid test, the subject may be offered the opportunity to repeat the 6MWT. The retest may occur immediately after the completion of the invalid 6MWT (following a rest period – minimum of 10 minutes) or the next day, based upon the judgment of the physical therapist and the investigator.

10.2.20.2. Gower's Maneuver

This test involves measuring the time it takes a subject lying supine on the floor to get to a standing position. Subjects may use the floor or their legs, but the test must be performed without the assistance of any furniture.

10.2.20.3. Timed Up and Go (TUG)

The general information regarding Timed Up and Go; a timed test used to assess mobility (TUG) has been derived from Podsiadlo and Richardson (1991). The test involves a seated subject getting up from a standard armchair, walking to a line that is 3 meters (9.8 feet) long, turning around at the line, walking back to the chair, and sitting back down. The test begins when the subject's buttocks begins to lift from the seat and ends when the subject's buttocks touches the seat.

10.2.20.4. 10-Meter Walk Test (10MWT)

This timed walk test should be performed with walking shoes on a flat surface. The purpose of this test is to traverse the distance of 10 meters as fast and safely as possible.

10.2.20.5. 4-Stair Climb

This test is performed with the use of “4 standard stairs.” This test will document the time to climb 4 standard stairs and will assist in assignment of the appropriate lower extremity functional grade for those individuals who are ambulatory.

10.2.20.6. Gait, Stairs, Gower, and Chair Maneuver (GSGC) Score

The GSGC score is obtained by adding the scores attributed to each functional test (gait by walking 10 meters, climbing 4 stairs, Gower’s maneuver, and rising from a chair) according to how the subject performed them and might vary from a minimum of 4 (normal performance) to a maximum of 27 (worst score).

10.2.21. Muscle Strength Tests – All Subjects

Manual muscle strength will be tested by medical research criteria (MRC) scale. All efforts should be made to maintain the same rater and method throughout the subject’s participation in the study. Muscle strength will also be measured using a hand-held dynamometer. Muscle groups tested include shoulder abductors, shoulder adductors, hip flexors, hip abductors, hip adductors (for hip adductors, hand held dynamometer only), knee extensors, knee flexors, elbow extensors, and elbow flexors.

Nonambulatory subjects will perform muscle strength tests for upper limbs only.

These assessments will be performed at baseline and Stage 3 and 4 as indicated in [Table 9](#), [Table 10](#), [Table 11](#), [Table 12](#), and [Table 13](#).

Detailed instructions for these tests will be provided in a separate study procedure manual.

10.3. Biological Specimen

Any biological specimens remaining at the end of the study may be used for future exploratory analyses to improve the understanding of Pompe disease and its management. The retention of samples is optional; subjects will have the option to agree or refuse to have their samples retained. Future genetic testing will not be conducted for retained samples.

10.4. High Sustained Antibody Titer

High sustained antibody titer is defined as subjects with anti-GAA antibody titer of 1:51,200 or higher from the 2 most recent tests using Genzyme’s or comparable method prior to screening. If a comparable method is used, it should be discussed with the Amicus Medical Monitor.

10.5. Infusion Only Visits

In Stage 3 and 4, ATB200 is to be administered every 2 weeks as an IV infusion in combination with oral AT2221. Changes in the protocol prescribed duration of ATB200 infusion due to safety or tolerability issues will be documented in the eCRF. During these Infusion Only Visits, in addition to receiving the study treatment, AE/SAE will be collected. Each site should follow their facility guidelines for performing infusions to monitor vital signs or other safety processes that may be in place. These Infusion Only Visits are not outlined in the Schedule of Assessments.

10.6. Home Infusion

Subjects participating in the study will be considered eligible for administration of ATB200/AT2221 on location at their home or residence after having received ATB200/AT2221 administrations in the study for a period of at least 6 months and not having experienced an IAR for a period of 6 months prior to last infusion. Subjects with history of severe IARs are not eligible for home infusions; subjects with a history including a life-threatening IAR are not eligible for home infusions. Eligible subjects may request participation in the Home Infusion Program with requests granted on a case-by-case basis following discussion between the Medical Monitor and PI with prior approvals granted by Institutional Review Boards (IRBs)/Ethics Committees (ECs), and Regulatory Authorities (RAs). Administration of ATB200/AT2221 will be performed at home for eligible subjects by a trained research home infusion nurse provided by an Amicus designated service provider. All subjects participating in the Home Infusion Program, will be required to complete all functional assessments at their primary site as defined in the protocol. Safety monitoring at home including reporting of AEs, SAEs, and IARs is performed by home infusion nurse. Refer to Section 11.1.3 for further information on IARs, including their reporting and management. The home infusion nurse will document and report the findings direct to sites after every infusion as detailed in the manual for home infusion.

Pre-requisites Criteria:

Inclusion Criteria:

- Received ATB200/AT2221 treatment for a minimum of one year
- Meets following requirements regarding feasibility of the home site for ERT infusion:
 - Availability of utilities and equipment required for storage of Drug Product upon receipt
 - Accessibility for delivery of Drug Product and associated supplies
 - Accessibility of trained home infusion nurse for preparation/administration
 - Preparation of ATB200 lyophilized drug product for reconstitution
 - Infusion of large volume parenteral product
 - Disposal of waste and discarding of used medical supplies
- Amicus/designee deems the home site to be appropriate for home infusion following home assessment
- PI agrees to collaborate with the home infusion agency/home infusion nurse with respect to providing advice and support as needed by the home infusion nurse

Exclusion Criteria:

- Any IAR in the past 6 months or recurrent severe or life-threatening IAR including anaphylaxis at any time.

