Subjects participating in the study will be considered eligible for administration of ATB200/AT2221 at their home after 6 months of ATB200/AT2221 infusions in the study and without an IAR for a period of 6 months prior to last infusion. Subjects with history of recurrent severe or life-threatening IARs including anaphylaxis are not eligible for home infusions. Eligible subjects may request participation in the Home Infusion Program with requests granted on a case-by-case basis following discussion between the Amicus Medical Monitor and Principal Investigator with prior approvals from Institutional Review Boards (IRBs)/Ethics Committees (ECs), and Regulatory Authorities (RAs). Administration of ATB200/AT2221 will be performed at home for eligible subjects by a trained home infusion nurse provided by an Amicus designated home infusion service provider. All subjects participating in the Home Infusion, will be required to complete all functional assessments at the investigational site as defined in the protocol.

Number of Subjects (Planned): Approximately 18 to 34 subjects will enroll in the study. Approximately 10 to 12 subjects in Cohort 1, 4 to 6 subjects in Cohort 2, 5 subjects in Cohort 3, and approximately 6 to 8 subjects in Cohort 4.

Diagnosis and Eligibility Criteria: At the Screening Visit for Stages 1 and 2, subjects from Cohort 1 will be evaluated using the eligibility criteria outlined below. At the Screening Visit for Stage 3, subjects from Cohorts 2, 3, and 4 will be evaluated with the eligibility criteria outlined below as well. Each subject must meet all of the inclusion criteria and none of the exclusion criteria. Waivers of inclusion/exclusion criteria are not permitted.

Inclusion/Exclusion Criteria**Cohort 1****Inclusion Criteria**

1. Male and female subjects between 18 and 65 years of age, inclusive
2. Subject must provide signed informed consent prior to any study-related procedures
3. Subjects of childbearing potential must agree to use medically accepted methods of contraception during the study and for 90 days after last co-administration of ATB200 and AT2221
4. Subject has a diagnosis of Pompe disease based on documented deficiency of GAA enzyme activity or by *GAA* genotyping
5. Subject has received ERT with alglucosidase alfa (Myozyme/Lumizyme) for the previous 2 to 6 years, inclusive
6. Subject is currently receiving alglucosidase alfa (Myozyme/Lumizyme), at a frequency of once every other week

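### The protocol's home-infusion rules disagree in three places: minimum prior treatment, the condition for 1-hour observation, and whether a single severe IAR is disqualifying

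*Protocol*

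**What the plan says.** **Minimum prior treatment.** The synopsis makes subjects eligible "after 6 months of ATB200/AT2221 infusions in the study and without an IAR for a period of 6 months prior to last infusion". The paragraph in Protocol Section 10.6 agrees on the treatment period: "having received ATB200/AT2221 administrations in the study for a period of at least 6 months". The inclusion list under the same heading requires something longer: "Received ATB200/AT2221 treatment for a minimum of one year".

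**Severe reactions.** The Section 10.6 paragraph states "Subjects with history of severe IARs are not eligible for home infusions" and continues "subjects with a history including a life-threatening IAR are not eligible for home infusions". The exclusion list that follows it reads "Any IAR in the past 6 months or recurrent severe or life-threatening IAR including anaphylaxis at any time". The synopsis reads "Subjects with history of recurrent severe or life-threatening IARs including anaphylaxis are not eligible for home infusions".

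**Observation at home.** Both the synopsis (Safety Monitoring) and Section 8.2 require 2 to 4 hours of monitoring for at least the first 3 months after a switch to home infusion, and both then allow 1 hour at the PI's discretion. The synopsis makes this conditional on there being neither IARs nor other AEs in those 3 months. Section 8.2 mentions IARs only.

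**Approval.** Section 10.6 has "requests granted on a case-by-case basis following discussion between the Medical Monitor and PI", with prior ethics and regulatory approvals.

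**The concern.** These rules decide who may be infused outside a hospital or infusion center, when, and for how long they are watched afterwards. At home, safety monitoring is done by the infusion nurse. Two sites that each follow the protocol faithfully could decide differently for the same subject, depending on which statement they consult. The protocol does not say which statement governs.

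**Working it through.** No design calculation applies. The check compares the current operative statements and asks whether one subject can receive two answers.

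| Rule | Synopsis | 10.6 paragraph | 10.6 lists | Section 8.2 |
|---|---|---|---|---|
| Minimum treatment | 6 months | 6 months | 1 year | not stated |
| Severe IAR bar | recurrent | any history (plural wording) | recurrent | not stated |
| Condition for 1 hour at home | no IAR and no other AE | not stated | not stated | no IAR |

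**1. Treatment minimum.** A subject IAR-free at month 8 qualifies under the synopsis and the paragraph but fails the inclusion list. With dosing every 2 weeks and none missed, the gap is (52 − 26 weeks) / 2 weeks = 13 infusions per subject.

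**2. Step-down.** Take a subject with no IAR in the first 3 months at home but one headache that the investigator does not regard as an IAR. The synopsis keeps this subject on 2 to 4 hours; Section 8.2 lets the PI reduce to 1 hour. The number of such subjects cannot be estimated from the documents.

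**3. Severe IAR.** Take a subject with one severe, non-anaphylactic IAR more than 6 months ago. The plain reading of the 10.6 paragraph bars this subject. The exclusion list does not, because the reaction is neither recent nor recurrent, and neither does the synopsis.

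This case can arise. Section 8.5 requires withdrawal for anaphylaxis by the Sampson criteria, but not for every severe reaction. Table 19 in Section 11.1.3 allows the infusion to be restarted 7 to 14 days after a severe reaction if the investigator thinks it appropriate.

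**4. Does choosing one text settle it?**
- Paragraph governs: 6 months, any severe IAR bars.
- Lists govern: 1 year, only recurrent severe IARs bar.
- Synopsis governs: 6 months, only recurrent severe IARs bar.
- All apply cumulatively: 1 year, any severe IAR bars.

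These are four different rule sets. The paragraph is the stricter text on severity and the list is the stricter on treatment time, so neither is simply the tighter version of the other.

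**5. How often.** Section 6.4.2.6 reports, at the August 2017 cut, 3 IARs in more than 400 infusions, so at most 3/400 = 0.75% of infusions. They occurred in two subjects, and AEs in that section are counted out of 20, giving 2/20 = 10% with any IAR. All three were skin symptoms. Their intensity is not given, and none is described as involving a vital organ, which is how Section 11.1.3 defines severe. These data predate Cohort 4 (6 to 8 planned, introduced with Amendment 5), so no count is projected.

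**The case against.** The strongest reply is that a careful site already has an answer on severe reactions. Exclusions normally apply together, and neither the synopsis nor the exclusion list says that a subject with one severe IAR is eligible. The paragraph also uses a plural for severe reactions beside a singular for a life-threatening one, so it may itself mean more than one. Both arguments soften the third conflict. Neither removes it: on the cumulative reading the synopsis shows only the looser rule, and on the plural reading the paragraph's meaning is left to the site.

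On treatment time, the Amendment 8.0 entry in the summary of changes records a move from 12 to 6 months. The one-year line therefore looks like a missed edit with a known intended value. That makes it editorial, but it is still the current inclusion criterion.

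Other safeguards stand: mandatory withdrawal for anaphylaxis, 6 IAR-free months, case-by-case approval, and PI discretion on step-down in both texts. They reduce the risk without saying which threshold applies.

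Three stronger readings are tempting:
- *The mismatch leaves part of the 2-hour IAR window in Section 11.1.3 unobserved.* It does not. One-hour observation is permitted under both texts and would remain after alignment. The 2-hour window is a reporting rule, not an observation requirement. Only the condition for step-down differs.
- *The protocol permits home infusion after one severe IAR.* No statement says so; two of the three merely fail to exclude it.
- *The analysis is compromised.* No endpoint or planned analysis depends on where the infusion was given.

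**Conclusion.** The inconsistency is real in three operative places. It is clearest for treatment minimum and step-down, and present but softer for severe IARs. It is a minor matter of internal consistency in safety conduct.

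The size is about 13 infusions per subject on the first point, an unknown but potentially larger number of subjects on the second, and probably few subjects on the third. This rests on uninterrupted two-weekly dosing for the infusion count, on the August 2017 IAR data being a fair guide to how rare severe reactions are, and on the plain reading of the 10.6 paragraph for the severe-IAR conflict. Alignment helps only while subjects are still being infused at home.

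**What to change.** - **Treatment minimum:** change the one-year line in the 10.6 inclusion list to 6 months, matching the paragraph and synopsis.
- **Step-down:** carry the synopsis condition (no IARs and no other AEs in the 3 months) into Section 8.2.
- **Severe IARs:** apply the stricter 10.6 paragraph in the synopsis and exclusion list. State explicitly that a single severe IAR bars home infusion, and whether IARs on prior ERT count. The latter matters because Section 10.2.3 collects past IARs with their intensity, and Cohort 4 enters with at least 7 years of ERT.

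This takes five short wording changes (inclusion line, Section 8.2, synopsis, exclusion list, and the clarified paragraph) or one clarification letter to sites. No new procedure is needed.

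The cost to subjects is that some stay on 2 to 4 hours of observation. Read literally, the synopsis condition would also count a missed dose, which Section 11.6.2 records as an AE. The few with one severe IAR would be kept on site infusion permanently, not merely for longer.

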11. ADVERSE EVENTS AND SERIOUS ADVERSE EVENTS

The definition of an AE is presented in Section 11.1.1. For each subject, reporting of AEs begins at the time written informed consent is provided. Investigators are responsible for reporting AE information to Institutional Review Boards (IRBs), International Ethics Committees (IECs), or Research Ethics Boards (REBs) in accordance with the requirements of their institutions.

11.1. Definitions

11.1.1. Adverse Events

An AE is any untoward medical occurrence in a subject administered a pharmaceutical product, biologic (at any dose), or medical device, which does not necessarily have a causal relationship with the treatment. Therefore, an AE can be any unfavorable and unintended sign (including an abnormal laboratory finding), symptom, or disease temporally associated with the use of a medical product, whether or not considered related to the medical product. Adverse events may include the onset of new illness and the exacerbation of pre-existing conditions.

The routine evolution of the disease condition under treatment according to the protocol will be evaluated as part of the disease symptoms assessments. Changes in Pompe disease symptoms must be reviewed by the investigator or a medically qualified sub-investigator and be recorded as “Clinically Significant” or “Not Clinically Significant” in subjects’ source records. Changes in the disease condition may not qualify as AEs. However, if there is a clinically relevant worsening of a sign or symptom of the condition under treatment and the outcome fulfills the definition of an AE, it must be reported as directed in the protocol.

Any AE that begins after the first dose of study medication (ATB200 and/or AT2221) will be considered a TEAE.

Subjects experiencing AEs should be followed until their health has returned to baseline status or stabilized or have otherwise been explained.

11.1.2. Serious Adverse Events

An SAE is any AE occurring at any dose that results in any of the following outcomes:

- Death.
- Life-threatening, as assessed by either the investigator or Amicus (places the subject at immediate risk of death from the AE as it occurs; it does not refer to an event which hypothetically might have caused death if it were more severe).
- Persistent or significant incapacity or substantial disruption of the ability to conduct normal life functions.
- Requires in-patient hospitalization (ie, admission to hospital, regardless of duration) or prolongs existing hospitalization.
 - Complications arising during hospitalization are AEs or SAEs, depending on nature of the event, and must be reported as described in this protocol.
 - Medications administered during hospitalization must be recorded in the Concomitant Medications eCRF module.

- Hospitalization for elective treatment of a pre-existing condition that did not worsen from baseline does not have to be reported as an SAE provided the planned treatment is documented in Screening Visit source records. If not documented in the Screening Visit source records, an SAE report is required. Outpatient procedures performed in a hospital do not qualify as an SAE.
- Is a congenital anomaly/birth defect.

An important medical event that may not result in one of the above serious outcomes may be considered an SAE when, based upon appropriate medical judgment, it may jeopardize the subject and may require medical or surgical intervention to prevent one of the serious outcomes. Examples of such medical events include allergic bronchospasm requiring intensive treatment in an emergency room or at home, blood dyscrasias, or convulsions that do not result in in-patient hospitalization, or development of drug dependency or drug abuse.

For all subjects, AEs and SAEs will be reported from time of informed consent signing, until 30 days after end of study participation.

11.1.3. Infusion-associated Reactions

An IAR is a disorder characterized by 1 or more adverse reaction(s) to the infusion of pharmacological or biological substances. These reactions are classified into 2 major subtypes, immediate and late, according to the time interval between the infusion and the onset of an infusion-related AE.

The reactions are divided into 5 severity grades as follows:

1. Mild (requires observation only); for example, transient flushing or rash
2. Moderate (minimal, usually oral, intervention suffices); for example, urticaria/myalgia/drug fever
3. Severe (vital organ involved yet not in a life-threatening manner; usually requires parenteral medication); for example, bronchospasm/angioedema/hypotension
4. Life-threatening (multisystem involvement of vital organs, urgent and critical care required); for example, systemic anaphylactic reaction
5. Death

Immediate-type IARs commonly involve 1 or more of the following systems: skin (urticaria and erythema), eyes (conjunctivitis), nasopharynx (rhinorrhea, rhinitis), bronchopulmonary tissues (wheezing, bronchospasm), and gastrointestinal tract (diarrhea, vomiting).

Late-type reactions first manifest more than 24 hours post infusion, usually 1 to 3 days post infusion. The most common symptoms of late-type infusion reactions are pruritic skin eruptions, fever, malaise, and polyarthralgia.

Any symptom or sign occurring during or within 2 hours of completion of the infusion should be reported as an immediate-type IAR and deemed drug-related AE, unless an alternative obvious explanation exists, eg, mechanical fall. Any symptom or sign occurring between 2 and 24 hours will be recorded as an IAR if it fits within the description of an IAR in the investigator's opinion. It would be reported as immediate-type IAR and deemed a drug-related AE.

Any symptom or sign occurring between 24 and 96 hours after completion of the infusion that, in the investigator's opinion, fits the clinical description of a symptom or sign associated with an IAR should be reported as a late-type IAR and deemed a drug-related AE.

A symptom or sign that occurs 24 hours or later and in the investigator's opinion is possibly, probably, or likely an IAR should be reported as such and deemed drug-related AE.

Note: The list of IAR symptoms provided in [Table 19](#) is not comprehensive. It is meant to serve as a guideline to the investigators to report and manage IAR as AE. [Table 19](#) also provides a guideline for management of IARs and anaphylaxis (see also [Appendix 1](#)). It is at the investigator's discretion to follow the guidelines or implement treatment protocol that their center is accustomed to following.

In the event that a subject experiences an IAR, the subject should be premedicated for subsequent infusions with antihistamines, steroids, and/or acetaminophen. The premedications should be continued for a period of up to 1 year. Decision regarding discontinuation of premedications should occur only after discussion with Amicus Medical Monitor.

Table 19: Guidelines for Management of Immediate Infusion-associated Reactions

Severity	Symptoms (such as, but not restricted to)	Management Guidelines
Mild reaction	Flushing Nausea Mild headache Tachycardia (pulse < 100 bpm) Abdominal pain	
REDUCE INFUSION RATE BY 50%
 
Contact investigator.
 
Give oral antihistamine/acetaminophen/paracetamol and/or IV antihistamine.
 
Prepare emergency equipment for any subsequent study treatment escalation.
 
Subject must be observed at site or medical facility for 2-4 hours after resolution of the symptoms.
 
Record all details of times, concomitant medications, and infusion rates.
 
Draw IgE and total GAA sample 6 to 8 and 24 hours after the start of the infusion reaction (2 samples).
 
IF SYMPTOMS PERSIST:
 
STOP THE INFUSION
 
After 30 minutes, if subject has improved, increase to previous infusion rate on direction of investigator/designee.
 
If subject has not improved after 60 minutes, consult with investigator as to whether additional medications should be administered.
 
If subject reacts for second time after return to the prior infusion rate, reduce rate by 50% and contact investigator/designee.
 
IF IN DOUBT, STOP INFUSION

Table 19: Guidelines for Management of Immediate Infusion-associated Reactions (Continued)

Severity	Symptoms (such as, but not restricted to)	Management Guidelines
Moderate reaction	Localized itchiness, and/or raised Urticarial rash (hives) Severe headache Fever or shivering Tachycardia (pulse > 100 bpm) Tachypnea Flushing Nausea Irritability Headache Vomiting Diarrhea Abdominal cramps Myalgia	** STOP INFUSION ** Immediately contact investigator. Administer high-flow oxygen if respiratory symptoms/distress. Give IM or IV antihistamines (eg, promethazine 25 to 50 mg). Give IV fluid bolus if warranted. Give IV steroids (hydrocortisone 100 mg) on direction of PI/designee. Continue management as directed by the PI/designee. Watch for at least 1 hour after resolution of symptoms. If deemed appropriate by PI/investigator, resume study treatment infusion at reduced rate and prepare emergency equipment. If deemed appropriate by PI/investigator, infusion can be suspended and reinitiated 48 hours later with premedications and at the infusion rate that was last tolerated. Observe subject for a minimum of 6 hours after resolution of the event. Record all details. Report SAE if criteria for SAE reporting are met. Draw IgE and total GAA sample 6 to 8 and 24 hours after the start of the infusion reaction (2 samples).

Table 19: Guidelines for Management of Immediate Infusion-associated Reactions (Continued)

Severity	Symptoms (such as, but not restricted to)	Management Guidelines
Severe reaction, anaphylaxis, or anaphylactoid reactions	Chest pain Generalized urticarial/angioedema Symptomatic hypotension(subject feeling faint, paleness) Hoarseness of voice/laryngeal edema Bronchospasm	** STOP INFUSION ** Activate emergency response and immediately contact investigator. For chest pain and symptomatic hypotension, initiate emergency procedures. Administer high-flow oxygen or intubate and mechanically ventilate as appropriate. Give IM adrenaline 300 mcg EpiPen into thigh (avoid buttock). If no response, repeat dose in 5 minutes. Prepare infusion of adrenaline 3 mg/50 mL NS (60 µg/mL), if needed. Give IV fluids 10- to 20-mL/kg fluid bolus on direction of PI/designee. Give IV antihistamines (promethazine 25 to 50 mg in 10 mL WFI over 2 to 3 minutes). Give IV steroids (hydrocortisone 100- to 500-mg bolus IV injection; dilute in 10 mL NS for doses between 100 and 500 mg) and infuse over 2 minutes. Give nebulized beta-2 agonists with high-flow oxygen on direction of PI/designee. Administer other treatments and/or transfer patient to hospital/ ICU as recommended by investigator/ designee. Observe subject for a minimum of 24 hours after resolution of the event. If deemed appropriate by PI/investigator, study treatment infusion can be re-initiated 7 to 14 days with premedications and at the 4-hour duration. Draw IgE and total GAA sample 6 to 8 and 24 hours after the start of the infusion reaction (2 samples). Report SAE if criteria for SAE reporting are met.

Abbreviations: GAA = human acid α -glucosidase; IgE = immunoglobulin E; IM = intramuscular; IV = intravenous; NS = normal saline; PI = Principal Investigator; SAE = serious adverse event; WFI = water for injection

Sources: Vogel 2010; Sampson et al 2006

